4.1. Inclusion Criteria

Patient eligibility should be reviewed and documented by an appropriately qualified member of the investigator's study team before patients are included in the study.

Patients must meet all of the following inclusion criteria to be eligible for enrollment into the study:

1. Cytogenetic or PCR-based diagnosis of Ph+ CML or BCR-ABL1+ if Ph- (from initial diagnosis). NOTE: Ph- CML patients will not count towards the 150 patients for primary and secondary analyses, which include Ph+ CML patients only.

NOTE: All patients must have screening bone marrow (BM) cytogenetic analysis with conventional G banding performed within 30 days prior to study entry (unless CML disease status is proven to be MMR by quantitative reverse transcription polymerase chain reaction [qRT-PCR]). Examination of at least 20 metaphases is required.

2. Prior treatment with 1 or more TKIs for CML.
3. Any CML phase, as long as the patient is resistant to, intolerant of, or otherwise not appropriate for treatment with imatinib, dasatinib and/or nilotinib.

4. Eastern Cooperative Oncology Group (ECOG) Performance Status of 0 or 1 for CP patients, or 0, 1, 2, or 3 for 4th line CP (and beyond) and AP/ BP patients.
5. Adequate bone marrow function:
 - For 2nd and 3rd line CP CML patients:
 - Absolute neutrophil count $>1000/\text{mm}^3$ ($>1 \times 10^9/\text{L}$).
 - Platelets $\geq 75,000/\text{mm}^3$ ($\geq 75 \times 10^9/\text{L}$) absent any platelet transfusions during the preceding 14 days.
 - For 4th line CP and AP/BP CML patients:
 - Absolute neutrophil count $>500/\text{mm}^3$ ($>0.5 \times 10^9/\text{L}$).
 - Platelets $\geq 50,000/\text{mm}^3$ ($\geq 50 \times 10^9/\text{L}$) absent any platelet transfusions during the preceding 14 days.
6. Adequate hepatic and renal function:
 - AST/ALT $\leq 2.5 \times$ the upper limit of normal (ULN) or ALT/AST $\leq 5 \times$ ULN if attributable to liver involvement of leukemia.
 - Total bilirubin $\leq 1.5 \times$ ULN (unless the bilirubin is principally unconjugated and there is a strong suspicion of subclinical hemolysis (e.g. chronic hemolysis without clinical symptoms), or the patient has documented Gilbert's Disease);
 - Alkaline phosphatase $\leq 2.5 \times$ ULN.
 - Creatinine $\leq 1.5 \times$ ULN or estimated creatinine clearance (CrCL) $\geq 60 \text{ mL/min}$ as calculated using the standard method for the institution.
7. Able to take daily oral tablets.
8. Age ≥ 18 years.

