Appendix 1. Guidelines for Identifying Resistance and Intolerance

Definition criteria for Resistance

There are two categories of resistance:

- Primary resistance is the failure to achieve a response as established by the European LeukemiaNet (ELN) or National Comprehensive Cancer Network (NCCN) guidelines. Primary resistance will be further divided into primary hematologic resistance, which occurs in cases who fail to normalize peripheral counts within 3–6 months of initiation of treatment; or primary cytogenetic resistance, in patients who fail to achieve any level of cytogenetic response (CyR) at 6 months, a major CyR (MCyR) at 12 months or a CCyR at 18 months.³⁰
- Secondary resistance is defined as those who have previously achieved and subsequently lost their hematologic, molecular, or cytogenetic response in accordance with ELN/NCCN guidelines.^{31, 32}

Definition of Intolerance to therapy:^{33,34}

A patient is deemed to be intolerant to a TKI if one or more of the following criteria are met:

- Any life threatening Grade 4 non hematological toxicity.
- Any Grade 3 or 4 non hematological toxicity that persists despite dose reduction and optimal symptomatic measures.
- Grade 3 or 4 hematological toxicity that is unresponsive to supportive measures and would require dose reduction below the accepted minimal effective dose.
- Any combination of non hematological toxicities of any grade that persist despite supportive measures and in the patients and physician's opinion compromise quality of life to such an extent that a change of therapy is justified.

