2.1. Study Design

This is a single-arm, open-label, non-randomized, multi-center Phase 4 study to evaluate bosutinib (Bosulif®) in patients with CP/AP/BP Ph+ CML whose disease has failed prior treatment with commercially available TKIs due to drug resistance or intolerance, or are otherwise contraindicated for treatment with commercially available TKIs such as imatinib, dasatinib, or nilotinib (ie, presence of a BCR-ABL mutation or medical condition making commercially available TKIs unsuitable for a patient). Patients will receive bosutinib for at least 4 years from the time of first dose, unless disease progression, unacceptable toxicity, patient withdrawal of consent, death or Sponsor discontinuation of study. Patients discontinuing bosutinib prior to completing at least 4 years of therapy will be followed for survival until they complete at least 4 years of follow-up from the time of first dose. Patients completing at least 4 years of bosutinib with continued benefit may be switched to commercially available therapy at that time.

Patients are allocated to the cohort based on the derived assignment from the baseline disease stage and prior TKI therapy. Patients are either:

- CP Ph+ CML second line (CP2L) resistant or intolerant to imatinib, dasatinib, or nilotinib;
- CP Ph+ CML third line (CP3L) resistant or intolerant to imatinib and dasatinib, imatinib and nilotinib, or dasatinib and nilotinib;

- CP Ph+ CML fourth or later line (CP4L) resistant or intolerant to imatinib, dasatinib, and nilotinib;
- AP Ph+ CML second line (AP2L) resistant or intolerant to imatinib, dasatinib, or nilotinib;
- AP Ph+ CML third line (AP3L) resistant or intolerant to imatinib and dasatinib, imatinib and nilotinib, or dasatinib and nilotinib;
- AP Ph+ CML fourth or later line (AP4L) resistant or intolerant to imatinib, dasatinib, and nilotinib;
- BP Ph+ CML second line (BP2L) resistant or intolerant to imatinib, dasatinib, or nilotinib;
- BP Ph+ CML third line (BP3L) resistant or intolerant to imatinib and dasatinib, imatinib and nilotinib, or dasatinib and nilotinib;
- BP Ph+ CML fourth or later line (BP4L) resistant or intolerant to imatinib, dasatinib, and nilotinib, or
- Ph- CML.

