Patients will be summarized based on these cohorts or a combination of these cohorts (eg, CP with 1 or 2 prior lines of TKI therapy includes CP2L and CP3L, CP total includes CP2L, CP3L, and CP4L). AP (AP2L, AP3L, AP4L) and BP (BP2L, BP3L, BP4L) patients combined are known as advanced patients. All Ph- CML patients will be summarized separately. Patients who were both resistant and intolerant to the prior TKI or neither will be considered intolerant to that TKI for analysis purposes.

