6.2.5. Cross Intolerance

Patients who discontinued prior TKI therapy due to intolerance of imatinib, dasatinib, or nilotinib and who discontinue bosutinib due to the same AE or AE cluster will be classified as having cross intolerance.

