8.2.4.1. Baseline Characteristics

Listings of demography and baseline characteristics data will be provided. The baseline variables listed below will be summarized using descriptive statistics.

- Age in years;
- Race;
- Sex;
- Weight (kg);
- Height (cm);
- ECOG performance status;
- Cancer history (prior cancer history including CML, initial and current CML disease stage, duration since CML diagnosis);
- Prior cancer therapies (number of prior regimens for interferon, imatinib, dasatinib, and nilotinib), duration of prior therapy, and reasons for resistance/intolerance status of prior TKIs;
- Medical history by MedDRA System Organ Class (SOC) and PT.

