8.2.4.6. Cross Intolerance

The percentage of patients experiencing cross intolerance to imatinib, dasatinib, or nilotinib will be summarized overall and by AE. The recurrence percentage of those grade 3/4 TEAEs during treatment with bosutinib will also be estimated.

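### SAP 2.1 labels patients who were neither resistant nor intolerant to a prior TKI as intolerant, and drops the resistance of those who were both, so the baseline status summary would be misstated

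*SAP*

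**What the plan says.** SAP 2.1, after listing the cohorts, sets the labelling rule: "Patients who were both resistant and intolerant to the prior TKI or neither will be considered intolerant to that TKI for analysis purposes". It gives no reason for the rule.

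Protocol Appendix 1 defines intolerance by toxicity: "A patient is deemed to be intolerant to a TKI if one or more of the following criteria are met". Each listed criterion describes a hematological or non-hematological toxicity. Resistance is defined there separately, as failure to reach a response or loss of one.

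Entry does not require resistance or intolerance. Protocol 4.1 accepts "Any CML phase, as long as the patient is resistant to, intolerant of, or otherwise not appropriate for treatment with imatinib, dasatinib and/or nilotinib", and the design text in SAP 2.1 includes patients who have failed earlier TKIs "or are otherwise contraindicated for treatment with commercially available TKIs".

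The status is a planned output. SAP 6.3.1 lists resistance/intolerance status for prior TKIs as a baseline variable, and SAP 8.2.4.1 summarizes "reasons for resistance/intolerance status of prior TKIs".

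Cross intolerance has its own definition in SAP 6.2.5: "Patients who discontinued prior TKI therapy due to intolerance of imatinib, dasatinib, or nilotinib and who discontinue bosutinib due to the same AE". A shared cluster of events also qualifies. SAP 8.2.4.6 then says "The percentage of patients experiencing cross intolerance to imatinib, dasatinib, or nilotinib will be summarized overall and by AE", without naming the patients who form the denominator.

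**The concern.** The rule moves patients in one direction only. Someone with no qualifying toxicity on the prior TKI is reported as intolerant to it, and someone with documented resistance who was also intolerant is no longer reported as resistant. Reported intolerance can only rise and reported resistance can only fall.

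This matters because the study is single-arm and descriptive, so readers rely on the baseline table to judge who was treated and to set the results beside other data. The protocol itself treats the split as informative. Section 1.2.2 reports the second-line Study 200 results separately for imatinib-resistant patients (Week 24 major cytogenetic response 35.5%, n=186) and imatinib-intolerant patients (30.0%, n=80). Appendix 5 has different response tables according to whether first-line treatment was changed for intolerance or for failure.

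A second, conditional issue follows. SAP 2.1 defines intolerant for analysis purposes, and SAP 8.2.4.6 leaves its denominator open. A programmer could reasonably use the relabelled group there, and would then include patients who cannot show cross intolerance because they had no earlier intolerance.

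**Working it through.** **Plan figures.** The documents give no count of *both* or *neither* patients, so there is no plan figure on this point to reproduce. The one precision figure, in Protocol 9.1 (standard deviation at most 0.075 with 45 patients), reproduces as √(0.25/45) = 0.0745, but has no bearing here.

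**Step 1: the label against the definition.** For one prior TKI, let the shares be R (resistant only), I (intolerant only), B (both) and N (neither), with R + I + B + N = 1.

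- Any resistance = R + B. Reported resistant under SAP 2.1 = R. Difference = −B.
- Any intolerance under Appendix 1 = I + B. Reported intolerant under SAP 2.1 = I + B + N. Difference = +N.

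**Step 2: illustrative size in the baseline table.** Assumptions: 151 patients (106 in the 2nd/3rd-line cohort plus the minimum of 45 in the 4th-line cohort, from Protocol 1.2.3 and SAP 2), one status per patient, and assumed shares.

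| R / I / B / N | Any resistance → reported | Any intolerance → reported | Resistance hidden (B × 151) | Intolerance added (N × 151) |
|---|---|---|---|---|
| 50 / 50 / 0 / 0% | 50% → 50% | 50% → 50% | 0 | 0 |
| 40 / 45 / 10 / 5% | 50% → 40% | 55% → 60% | 15 | 8 |
| 35 / 40 / 15 / 10% | 50% → 35% | 55% → 65% | 23 | 15 |
| 30 / 35 / 20 / 15% | 50% → 30% | 55% → 70% | 30 | 23 |

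**Step 3: cross intolerance, under each possible denominator.** Assume 75 truly intolerant patients (including *both*) and a true rate of 20%, so the numerator is 0.20 × 75 = 15. By SAP 6.2.5 no *neither* patient can add to it.

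- Denominator = patients who stopped that TKI for intolerance: 15/75 = 20.0%. The label changes nothing.
- Denominator = everyone labelled intolerant under SAP 2.1, with 8, 15 or 23 *neither* patients added: 15/83 = 18.1%, 15/90 = 16.7%, 15/98 = 15.3%.

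The relative reduction is N/(T + N), where T is the number truly intolerant and N is now a count. With 23 *neither* patients it is 23/113 = 20% at T = 90 and 23/83 = 28% at T = 60, whatever the true rate.

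**Step 4: where the label is not used.** SAP 8.2.1 and 8.2.2 group efficacy by disease phase and line of therapy. The named subgroups in SAP 6.4 are gender, age and race. The analysis sets in SAP 5 rest on dosing and on a valid baseline assessment. Cohort assignment in SAP 2.1 comes from disease stage and prior TKI therapy, and its cohort descriptions accept either label, so moving a patient between the two does not change the cohort.

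**The case against.** The strongest reply is that this is a pre-stated convention for a two-level descriptive variable and that little depends on it. Patients who were both are in fact intolerant, so giving that label precedence is not false. Protocol 6.1 collects best response and specific intolerances for each prior CML therapy, and SAP 8.2.4.1 provides baseline listings and a summary of reasons, so the underlying information is kept. If nobody was both or neither, nothing changes.

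Much of this stands. Labelling *both* as intolerant is a loss of information rather than a false statement, and it does no harm in the cross-intolerance analysis, where those patients belong. The reply does not rescue the *neither* label, which conflicts with Appendix 1. Nor does the SAP say that either group will be shown separately in the summary.

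A reader might infer three stronger claims, none of which the documents support:

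- *The cross-intolerance tables are wrong.* The numerator needs an actual discontinuation for intolerance, and the denominator is unstated, so dilution is possible but not established.
- *The rule misstates the treated population as a whole.* It affects only the resistant/intolerant description; the analyses in step 4 do not depend on it.
- *Everyone admitted as "as long as the patient is resistant to, intolerant of, or otherwise not appropriate for treatment with imatinib, dasatinib and/or nilotinib" is relabelled.* The entry criterion can concern a TKI the patient never took. The SAP rule applies to each prior TKI actually received. A patient resistant to imatinib and contraindicated for nilotinib is resistant to imatinib, not *neither*. The two groups overlap but are not the same.

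**Conclusion.** The point holds for the baseline summary. Followed as written, the SAP 2.1 rule contradicts Protocol Appendix 1 for patients who were neither resistant nor intolerant, and hides resistance in patients who were both. Intolerance is overstated by exactly the *neither* share and resistance understated by exactly the *both* share. The direction is certain. The size is unknown, because the figures in the working rest on assumed shares and could be zero.

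For cross intolerance the finding is an unstated denominator. The effect is zero if the denominator follows SAP 6.2.5, and is a dilution only if the SAP 2.1 label is used instead.

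No primary or secondary efficacy estimate is affected. The correction is still worth making, since it is cheap and the affected table describes the patients in a single-arm study.

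**What to change.** 1. In SAP 2.1, replace the rule with four categories for each prior TKI: resistant only, intolerant only, both, and neither/other, using the Appendix 1 definitions.
2. In SAP 6.3.1 and 8.2.4.1, show all four categories in the baseline table, with reasons where they apply.
3. In SAP 8.2.4.6, state that the denominator for each TKI is the patients who discontinued it due to documented intolerance, including those who were also resistant. This agrees with SAP 6.2.5 and keeps *neither* patients out.
4. Because the cohort descriptions in SAP 2.1 speak of patients resistant or intolerant to each TKI, add that a prior TKI counts towards the line of therapy whichever category applies, so that cohort membership does not change.

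The cost is SAP wording and a few table rows. The response and tolerability history for each prior therapy is already collected under Protocol 6.1, so no new data should be needed.

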2.2. Study Objectives

Primary Objectives

- *To estimate the 1-year (52-week) probability of cumulative confirmed Major Cytogenetic Response (MCyR) in CP Ph+ CML patients with 1 or 2 prior lines of TKI therapy.*
- *To estimate the 1-year (52-week) probability of cumulative confirmed MCyR in CP Ph+ CML patients with 3 or more prior lines of TKI therapy.*
- *To estimate the 1-year (52-week) probability of cumulative confirmed Overall Hematological Response (OHR) in AP and BP Ph+ CML with any prior TKI therapy.*

Secondary Objectives

- *To estimate the cumulative probability of MCyR in each disease phase (CP, AP and BP) for Ph+ CML patients.*

- *To estimate the cumulative probability of confirmed OHR in each disease phase (AP and BP) for Ph+ CML patients by number of lines of prior therapy.*
- *To characterize the distributions of best response (molecular, cytogenetic, or hematologic) in the CP, AP, and BP Ph+ CML patient populations.*
- *To estimate the probability of MCyR at 3, 6, 12, 18, and 24 months in the CP, AP, and BP Ph+ CML patient populations.*
- *To estimate the probability of confirmed OHR at 3, 6, 9, 12, 18, and 24 months in the AP and BP Ph+ CML patient populations.*
- *To estimate the probability of cumulative confirmed complete hematologic response (CHR) in the CP, AP and BP Ph+ CML patient populations.*
- *To estimate the probability of cumulative MMR in the CP, AP, and BP Ph+ CML patient populations.*
- *To estimate the duration of CCyR.*
- *To estimate the duration of MMR.*
- *To evaluate the overall safety profile of bosutinib in the study population.*

Exploratory Objectives

- *To obtain preliminary estimates of Progression Free Survival (PFS) and Overall Survival (OS) in 4th or later line CP, AP and BP Ph+ CML patients.*
- *To identify BCR-ABL mutations associated with sensitivity or resistance to bosutinib, as well as to catalog possible acquired resistance mutations.*
- *To explore efficacy (hematologic and molecular response) in Ph- CML patients.*
- *To evaluate patient reported outcomes measures.*
- *To collect banked biospecimens for exploratory research, unless prohibited by local regulations or ethics committee decision.*

3. INTERIM ANALYSES, FINAL ANALYSES AND UNBLINDING

There are no interim analyses planned for this study. The analysis for the primary objective will be done after all patients have completed one year of follow-up and all data through one year have been collected and processed. There will be one follow-up analysis when all study data are complete.

This is a single-arm, open-label study so unblinding is not required.

4. HYPOTHESES AND DECISION RULES

4.1. Statistical Hypotheses

There are no statistical hypotheses in this study.

4.2. Statistical Decision Rules

There are no statistical decision rules for this study and no hypothesis testing will be done.

5. ANALYSIS SETS

5.1. Full Analysis Set

The full analysis set is all patients who receive at least one dose of bosutinib. This is the same as the safety analysis set.

5.2. ‘Per Protocol’ Analysis Set

Per Protocol analyses will not be performed in this study.

5.3. Safety Analysis Set

The safety analysis set is all patients who received at least one dose of bosutinib. This is the same as the full analysis set thus only the “full analysis set” terminology will be used.

5.4. Other Analysis Sets

The evaluable analysis set are those treated patients with a valid baseline efficacy assessment for the respective endpoint (ie, [1] at least 20 metaphases from the baseline bone marrow cytogenetic assessment or a CCyR with at least 200 cells analyzed from the fluorescence in situ hybridization [FISH] baseline assessment or MMR from the baseline molecular assessment for cytogenetic endpoints or [2] a valid baseline hematologic assessment for hematologic endpoints as defined in [Appendix 1](#) or [3] a valid baseline molecular assessment from the central laboratory for molecular endpoints).

5.5. Treatment Misallocations

B1871039 is a single arm study so there will be no treatment misallocations. Patients who are enrolled but not treated will not be included in the safety or efficacy analyses.

5.6. Protocol Deviations

The full list of protocol deviations for the study report will be compiled prior to database closure. A listing of COVID-19 related protocol deviations will be provided.

6. ENDPOINTS AND COVARIATES

In general, the baseline value will be defined as the last non-missing value prior to first dose, unless specifically stated otherwise. Assessments performed on Week 1 day 1 will be assumed to be pre-dose per the schedule of activities in the Protocol.

An on-treatment evaluation is defined as any evaluation done during bosutinib therapy or within 28 days of last dose.

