5.6.1. Prohibited

All concomitant medication restrictions apply only while the patient is on the active treatment phase of the study (i.e., receiving bosutinib), and include:

- Any anti-leukemia treatment other than the regimen defined in this protocol, including donor lymphocyte infusions;
- Any other investigational agents while the patient is receiving bosutinib;
- Prophylactic use of growth factors;
- Requiring concurrent treatment with immunosuppressive agents, other than corticosteroids prescribed for a short course of therapy (≤ 10 days).

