6.4. Long-Term Follow-Up Visit

Patients who discontinue from treatment for any reason (except death, withdrawal of patient consent or termination of study by Sponsor) prior to completing at least 4 years will enter into the follow-up phase of the study. Patients will be followed for at least 4 years from the first dose of bosutinib and will be assessed for overall survival status only.

Follow-up will be conducted approximately every 3 months from the last dose of bosutinib (telephone calls acceptable). If bone marrow transplantation is performed after discontinuation, it should be captured during the long-term follow-up as well as treatment with another TKI, time to progression, and transformation to AP or BP.

Patient study participation will not conclude before 4 years after the first dose of bosutinib was administered.

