8.1.4.2. Recording Non-serious AEs and SAEs on the CRF

During the active collection period, both non-serious AEs and SAEs are recorded on the CRF.

Follow-up by the investigator may be required until the event or its sequelae resolve or stabilize at a level acceptable to the investigator, and Pfizer concurs with that assessment.

If a patient begins a new anticancer therapy, the recording period for non-serious AEs ends at the time the new treatment is started; however, SAEs must continue to be recorded on the CRF during the above-indicated active collection period.

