6.1. Efficacy Endpoint(s)

Primary

- *Cumulative confirmed MCyR defined as Complete Cytogenetic Response (CCyR) or Partial Cytogenetic Response (PCyR) by 1 year (52 weeks) in 2nd and 3rd line CP patients.*
- *Cumulative confirmed MCyR by 1 year (52 weeks) in 4th and later line CP patients.*
- *Cumulative confirmed OHR defined as Complete Hematological Response (CHR) or Return to Chronic Phase (RCP) by 1 year (52 weeks) in AP and BP patients.*

The local cytogenetic assessments will be used for the primary endpoint analysis in CP patients. The local hematologic assessments will be used for the primary endpoint analysis in AP and BP patients.

Cumulative response is any response on-treatment up through Week 52 (based on the date of assessment) with a 4 week window (\leq Week 56). Response is confirmed for cytogenetic and hematologic with 2 consecutive responses at least 28 days apart. The date of confirmed response is the date of the first response. Cytogenetic and hematologic responses are defined in [Appendix 2](#) and [Appendix 1](#). MCyR is defined as a CCyR or PCyR. OHR is defined as CHR or RCP. To be considered a responder, the patient must have maintenance of baseline response for \geq 5 weeks for hematologic response or \geq 52 weeks for cytogenetic response or an improvement from baseline. Patients with PCyR at baseline must attain CCyR on-treatment to be counted as a cytogenetic responder. Patients with at least MMR and a deeper molecular response than baseline are counted as confirmed CCyR.

Secondary

- *Cumulative MCyR in CP, AP and BP patients.*
- *Cumulative confirmed OHR in AP and BP patients by line of therapy.*
- *Cumulative best response in CP, AP, and BP patients.*
- *MCyR at 3, 6, 12, 18, and 24 months in CP, AP, and BP patients.*
- *Confirmed OHR at 3, 6, 9, 12, 18, and 24 months in AP and BP patients.*
- *Cumulative confirmed CHR.*
- *Cumulative MMR in CP, AP, and BP patients.*
- *Duration of CCyR.*
- *Duration of MMR.*

The local cytogenetic assessments will be used for the secondary endpoint analyses for all patients. The local hematologic assessments will be used for the secondary endpoint analyses for all patients. *Molecular assessments will be performed at a central laboratory. Endpoint analysis for molecular response will be carried out by independent central analysis.*

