6.2. Safety Endpoints

Treatment-emergent adverse events (TEAE) are defined as any event increasing in severity from baseline or any new event starting during bosutinib therapy or within 28 days of the last dose of study drug (using 28 day lag).

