6.2.6. Death

Death data will be collected during this study. Mandatory variables captured are date of death and cause of death. Deaths within 28 days of last dose and death due to study treatment toxicity are safety endpoints.

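### The SAP's 28-day post-dose on-treatment window for efficacy does not close when another anti-leukemia therapy starts, so a post-switch sample can be credited to bosutinib

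*SAP*

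**What the plan says.** SAP section 6 sets one window for all evaluations: "An on-treatment evaluation is defined as any evaluation done during bosutinib therapy or within 28 days of last dose". SAP 6.1 builds cumulative response on it. The primary endpoint counts on-treatment responses up to Week 56, and the secondary endpoints count them at any time on treatment. Primary cytogenetic and hematologic responses need two consecutive assessments at least 28 days apart. The primary definition also has a molecular route: "Patients with at least MMR and a deeper molecular response than baseline are counted as confirmed CCyR". Secondary cytogenetic and molecular responses need no confirmation. SAP section 7 allows CCyR to be imputed from an MMR on the same date when PCR replaced cytogenetics. Duration of response and PFS are censored at the last assessment that could be evaluated.

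On the treatment side, Protocol 5.6.1 says: "All concomitant medication restrictions apply only while the patient is on the active treatment phase of the study". Protocol 6.3 puts the End of Treatment visit, including central qRT-PCR and hematology, within 28 days of the last dose. Protocol 6.4 says of a transplant after discontinuation that "it should be captured during the long-term follow-up as well as treatment with another TKI". SAP 6.2.4 classes any drug taken in those 28 days as concomitant.

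On safety, SAP 6.2 counts as treatment-emergent "any new event starting during bosutinib therapy or within 28 days of the last dose of study drug (using 28 day lag"), and SAP 6.2.6 adds: "Deaths within 28 days of last dose and death due to study treatment toxicity are safety endpoints". After a switch, Protocol 8.1.4.2 says "the recording period for non-serious AEs ends at the time the new treatment is started; however, SAEs must continue to be recorded" through the active collection period.

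**The concern.** The ban on other anti-leukemia drugs ends with bosutinib, but the on-treatment window runs 28 days longer. A patient may start the next TKI the day after the last dose and attend the End of Treatment visit some weeks later. Nothing in the SAP's endpoint, missing-data or analysis sections excludes that sample or censors before it.

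The plan already accepts that an assessment made under another active agent should not be used. Hydroxyurea and anagrelide must be stopped 72 hours before any disease assessment (Protocol 4.2 and 5.6.2). Counts within a week of G-CSF or a platelet transfusion are not evaluable (Protocol 7.1.1.2; SAP Appendix 2). A new TKI, chemotherapy or transplant after the last dose has no such rule.

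The study is single-arm and supports conversion of a conditional approval, so no control group shares the error. A response first reached on the next drug would raise the rate reported for bosutinib.

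**Working it through.** **The plan's own figure.** Protocol 9.1 says the standard deviation of a response estimate with 45 patients is at most 0.075. At p = 0.5, sqrt(0.5 × 0.5 / 45) = 0.0745, which agrees. The issue here does not alter it.

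**Can a confirmed response arise wholly after the last dose?** Call the last-dose day 0. The window then runs to day 28. Two assessments at least 28 days apart, both on days 1 to 28, do not exist, since the widest gap is 27 days. With day 0 included, the only pair is day 0 and day 28. For a confirming assessment on day k, the first response must fall on day k − 28 or earlier, so never after day 0. A post-switch assessment can confirm a cytogenetic or hematologic response first seen on bosutinib, but it cannot supply both halves.

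**Routes that remain open for the primary endpoint**
1. Molecular route: the SAP asks for no second assessment, so one post-switch PCR that first reaches MMR and is deeper than baseline is enough.
2. Confirmation: as above, the second of the two assessments only.
3. Maintenance: a patient with CCyR at baseline must hold it for at least 52 weeks. Because 28 days is 4 weeks, a patient whose last dose falls between Week 48 and Week 52 could complete the requirement with a post-switch assessment.

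**Routes for the other endpoints**
- Unconfirmed MCyR, MMR and best response: one post-switch sample is enough. End of Treatment marrow is required only after progression or failure (Protocol 6.3), so the usual vehicle is PCR, with CCyR imputed from MMR.
- Time to response: the first response date can be a post-switch date.
- Duration of response and PFS: a post-switch sample can move the censoring date later. Inside the window the shift is at most 28 / 30.4 = 0.92 months per censored patient, using the SAP's divisor. A post-switch result can also help confirm a loss of response, or prevent its confirmation, so the direction for duration is not fixed.

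**Scale.** The documents give no count of patients who start a new therapy within 28 days, so no corrected rate can be computed. The table assumes a response rate near 50% and removes 1 to 3 responders, with exact 95% intervals.

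| Responders removed | n = 45 | n = 106 |
|---|---|---|
| 0 | 22/45 = 48.9% (33.7 to 64.2) | 53/106 = 50.0% (40.1 to 59.9) |
| 1 | 46.7% (31.7 to 62.1), −2.2 points | 49.1% (39.2 to 59.0), −0.9 |
| 2 | 44.4% (29.6 to 60.0), −4.4 | 48.1% (38.3 to 58.0), −1.9 |
| 3 | 42.2% (27.7 to 57.8), −6.7 | 47.2% (37.4 to 57.1), −2.8 |

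One patient of 45 is 2.2 / 7.45 = 0.30 of the maximum standard error. The figures 45 (fourth or later line) and 106 (second and third line) each mix CP, AP and BP. The endpoint denominators are smaller, and one patient weighs more in them.

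**The case against.** The strongest defence is that few patients can be affected. Under the response milestones in Protocol Appendix 5, a transcript level of 10% or less is the optimal molecular result at month 3, and after intolerance MMR is the optimal result only at month 12. A first MMR caused by less than four weeks of a new drug would be far ahead of that. A patient close to MMR at the switch got there largely on bosutinib. End of Treatment procedures may be skipped if done in the previous 6 weeks. PFS progression must be the recorded reason for stopping treatment. Time to response is analysed with discontinuation as a competing risk. All of this stands and supports a small number. It does not supply the missing rule.

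A reader might go further and infer that every SAE or death after a switch is wrongly blamed on bosutinib. The documents do not support that. Treatment-emergent is a label of timing. Causality is judged separately by the investigator (SAP 6.2.7), related events have their own summary (SAP 8.2.4.8), and causes of death within 28 days are reported (SAP 8.2.4.7). Protocol 8.1.4.1 keeps SAE reporting going whatever treatment intervenes, which is deliberate and conservative. Only SAEs are recorded after a switch, so ascertainment in the overlap is uneven, but no planned analysis compares serious with non-serious rates.

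A reader might also want deaths after a switch removed from duration of response and PFS. Protocol 9.2.2 counts death within 28 days of last dose as ending a response, and Protocol 9.3 counts death from any cause in PFS. Removing such deaths would contradict both and would favour bosutinib.

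**Conclusion.** The gap is real and confined to efficacy assessments. It matters most for unconfirmed MCyR, MMR, best response, and time to and duration of response. It reaches the primary endpoint only by the three narrow routes above. Each post-switch responder adds about 2.2 points per 45 patients or 0.9 per 106, and somewhat more in the actual denominators. How many there are is unknown and probably small.

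Two larger figures are tempting. SAP 8.2.2 says more than 80% of patients were off treatment by the COVID-19 anchor date, and 0.80 × 150 = 120. That counts everyone off treatment, possibly including patients who completed four years, so it does not measure exposure to another drug. One could also assume that 20 to 35% stop in year 1 and that 30 to 70% of those switch within 28 days: 150 × 0.20 × 0.30 = 9, and 150 × 0.35 × 0.70 = 37. Neither range is in the documents. The product counts patients who switch. A false responder must also have a sample taken after the new drug starts, and that sample must newly meet the response definition.

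**What to change.** In SAP section 6, for efficacy assessments only, end the on-treatment window at the earlier of 28 days after the last bosutinib dose and the day before the start of any new anti-leukemia therapy or transplant. Apply this to response, to loss of response, and to the last-assessment censoring date for duration of response and PFS. If the one-year primary analysis has already been done, report the result as a sensitivity analysis of it.

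Keep deaths within 28 days as events for duration of response and PFS, as the protocol defines them. Keep all SAEs and deaths within 28 days in the main TEAE and death tables. Add only a flag or a supplementary listing for those that begin after new therapy starts.

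The cost is a few sentences and one derived date. Most of the data should exist: Protocol 5.6 records concomitant treatments with their duration, and Protocol 6.4 captures later TKIs and transplant. Protocol 6.4 does not say that start dates are collected and does not name chemotherapy or donor lymphocytes, so this needs checking against the CRF. The small downside is that a few late assessments are dropped. Some responses may then lose their confirmation, and a response rate may be slightly lower.
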